The PK sub-study will assess nicotine uptake and urge to smoke from the *my*blu[™] products relative to combustible cigarettes and an e-cigarette comparator (JUUL[®]). A subset of up to 20 subjects assigned to each of the my bluTM e-liquids, 20 subjects from the continue-smoking arm, and all 20 subjects in the JUUL[®] arm will participate. Subjects in the JUUL[®] arm will begin using the product after check-in for Test Visit 1 and will continue to use the product through discharge on Day 1 from the study following the PK assessment (subjects in the JUUL® arm will only participate in the PK sub-study). PK assessments will be preceded by a minimum 10-hour abstention from product use and will take place on Day 1 for the JUUL® and continue-smoking arms, and on Day 5 for the *my*blu[™] arm. Product use for the PK assessments will consist of two sessions: 1) a fixed puffing session in the morning consisting of 10 puffs taken at 30 second intervals, with puffs 3 seconds in duration, and 2) an ad *libitum* use session beginning 6 hours after the start of the morning session and consisting of unlimited use of the e-cigarette product for 5 minutes or one cigarette, with no limits on puff duration or inter-puff interval. No product use of any kind will be allowed between the sessions. E-cigarette pods used for each session will be weighed before and after use to measure the amount of e-liquid used.

All product use during confinement will be documented by the clinic staff. Subjects in the mybluTM and continue-smoking arms will be required to self-report product use from Day 3 through discharge from the study.

Exhaled CO and urine cotinine measurements will be used to confirm smoking/nicotine use status prior to Day 1 and to assess subject compliance with product assignment requirements thereafter.

The clinic staff will contact all subjects via a telephone call approximately 14 days after discharge from the study (either as scheduled or after early termination) for reporting of AEs and use of concomitant medications.

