The PK sub-study will assess nicotine uptake and urge to smoke from the mybluTM products relative to combustible cigarettes and an e-cigarette comparator (JUUL®). A subset of up to 20 subjects assigned to each of the mybluTM e-liquids, 20 subjects from the continue-smoking arm, and all 20 subjects in the JUUL® arm will participate. Subjects in the JUUL® arm will begin using the product after check-in (Day -2) for Test Visit 1 and will continue to use the product through discharge on Day 1 from the study following the PK assessment (subjects in the JUUL® arm will only participate in the PK sub-study). PK assessments will be preceded by a minimum 10-hour abstention from product use and will take place on Day 1 for the JUUL® and continue-smoking arms, and on Day 5 for the *my*bluTM arm. Product use for the PK assessments will consist of two sessions: 1) a fixed/controlled puffing session in the morning consisting of 10 puffs taken at 30 second intervals, with puffs 3 seconds in duration, and 2) an *ad libitum* use session beginning 6 hours after the start of the morning session and consisting of unlimited use of the e-cigarette product for 5 minutes or one cigarette, with no limits on puff duration or inter-puff interval. No product use of any kind will be allowed between the sessions. E-cigarette pods used for each session will be weighed before and after use to measure the amount of e-liquid used.

All product use during confinement will be documented by the clinic staff. Subjects in the *my*bluTM and continue-smoking arms will be required to self-report product use from Day 3 through discharge from the study.

Exhaled CO and urine cotinine measurements will be used to confirm smoking/nicotine use status prior to Day 1 and to assess subject compliance with product assignment requirements thereafter.

The clinic staff will contact all subjects via a telephone call approximately 14 days after discharge from the study (either as scheduled or after early termination) for reporting of AEs and use of concomitant medications.

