Screening of subjects will occur within 28 days prior to prior to check-in (Day -2) for Test Visit 1. Screening safety evaluations will include a physical examination, vital signs, ECG, clinical laboratory tests (clinical chemistry, hematology, urinalysis, and serology), lung function, urine drug tests, urine cotinine tests, and alcohol breath tests, FSH tests (post-menopausal females) and serum and urine pregnancy tests (females only).

On-study safety evaluations will include a symptom-driven physical examinations, vital signs, ECG, clinical laboratory tests (clinical chemistry, hematology, and urinalysis), lung function, and urine pregnancy tests (females only).

AEs spontaneously reported by the subjects or observed by the Investigator or other study personnel will be documented and monitored from the time of first product use after successful completion of the check-in (Day -2) events for Test Visit 1 through the end of the Follow-up Period. Any prior and concomitant medications taken from 30 days prior to Screening through the Follow-up Period will also be recorded.

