# JUUL® Product Use

Subjects in the JUUL® arm will begin using the product following the demonstration and training on Day -2 and will continue to use the product through 23:00 on Day -1.

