#### 7.4 Adverse Events

All adverse events (AEs) occurring during this clinical trial will be coded using the Medical Dictionary for Regulatory Activities (MedDRA®), Version 21.0.

All AEs captured in the database will be listed in by-subject data listings including verbatim term, coded term, product, severity, relationship to study product, and action; however, only product use-emergent AEs (PUEAEs) will be summarized.

A PUEAE is defined as an AE that is starting or worsening at the time of or after the first randomized study product use. Each PUEAE will be attributed to a study product based on the onset date and time of the AE.

If the onset time of an AE is missing and the onset date is the same as the first study product use date, then the AE will be considered product use emergent in the study product. If onset time of an AE is missing and the onset date does not fall on a study product use date, then the AE will be considered product use emergent for the last study product administered. If the onset date of an AE is missing, then the AE will be considered product use emergent, unless the onset date is known to have occurred within or between specific product use days.

PUEAEs will be tabulated by System Organ Class (SOC) and Preferred Term. Summary tables will include number of subjects reporting the AE and as percent of number of subjects used study product by product. The number of AEs will be tabulated in a similar manner. Tables which tabulate the number of PUEAEs by severity and relationship to study product will also be included.

In addition, adverse events occurred during baseline period on Day -2 and day -1 will be summarized separately.

Serious adverse events (SAEs), if present, will also be listed. Applicable narratives will be included in the CSR.

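### AE tables show crude percentages by product over observation windows from about 17 to 71 days, and split switchers' time across two columns, with no person-time shown

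*SAP*

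**What the plan says.** SAP section 7.4 defines the summary statistic: "Summary tables will include number of subjects reporting the AE and as percent of number of subjects used study product by product". Events go to products by timing: "Each PUEAE will be attributed to a study product based on the onset date and time of the AE". If the onset time is missing and the onset date is not a product use date, "then the AE will be considered product use emergent for the last study product administered". That is the nearest the SAP comes to a rule for events in the follow-up period.

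The shells in SAP section 10.2 put Products A to F side by side. Table 14.3.1.1 gives subjects with an event as a percentage of those who used the product. Table 14.3.1.2 gives numbers of events, with percentages of all events. Events from the myblu trial period go to a separate Product Trial column. No shell shows person-time.

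On timing, SAP section 3 collects AEs from first product use after the check-in "events for Test Visit 1 through the end of the Follow-up Period". The JUUL arm "will begin using the product following the demonstration and training on Day -2" (SAP 6.1.1) and will "continue to use the product through discharge on Day 1 from the study following the PK assessment" (SAP section 3). These subjects "will only participate in the PK sub-study" (Protocol 3.1). Follow-up is the same length in every arm: "The clinic staff will contact all subjects via a telephone call approximately 14 days after discharge from the study". Myblu subjects use their assigned e-liquid from Day 3, may switch at Test Visit 3, and are discharged on Day 57 (SAP 6.1.1; Protocol 6.1.4).

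**The concern.** A crude percentage of subjects with an event grows with the time they are watched. When columns cover very different lengths of time, a difference between them mixes the event rate with the length of the window, and the reader cannot separate the two.

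Two comparisons are affected. The JUUL column covers roughly a quarter of the time of a myblu non-switcher. Within myblu, a switcher has used both products. On the wording of SAP 7.4 that subject counts in full in both denominators but gives each column only part of the observation time. Continue-smoking subjects stay in one column throughout. Switching therefore dilutes the myblu percentages relative to cigarettes, which bears on secondary objective 10, confirming myblu safety. The results may also be used in a premarket application (Protocol 1.3).

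**Working it through.** **Check of the calendar.** Days are counted inclusively, with no Day 0. The Protocol synopsis gives about 14 weeks from Screening to Follow-up for myblu and continue-smoking, and up to 7 weeks for JUUL.

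- Myblu and continue-smoking: 28 screening days + 59 days (Day -2 to 57) + 14 = 101 days = 14.4 weeks.
- JUUL: 28 + 3 days (Day -2 to 1) + 14 = 45 days = 6.4 weeks.

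Both agree with the stated durations.

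**Observation windows by product column**, taking follow-up events as belonging to the last product used:

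- JUUL: Day -2 to Day 15 = 17 days.
- Myblu non-switcher: Day 3 to Day 71 (57 + 14) = 69 days.
- Continue-smoking: Day 1 to Day 71 = 71 days.
- Switcher: Day 3 to 29 = 27 days on the first product; Day 30 to 71 = 42 days on the second.

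**JUUL against myblu non-switchers.** Assume the same constant hazard h in every column. The expected percentage over t days is 1 - exp(-h × t), so p69 = 1 - (1 - p17)^(69/17). As events become rare the ratio tends to 69/17 = 4.06.

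| JUUL | Myblu non-switcher | Ratio |
|---|---|---|
| 1% | 4.0% | 4.0 |
| 5% | 18.8% | 3.8 |
| 10% | 34.8% | 3.5 |
| 20% | 59.6% | 3.0 |
| 30% | 76.5% | 2.5 |

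Other readings of the windows do not close the gap:

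- The ±2-day call windows give 67/19 = 3.5 to 71/15 = 4.7.
- SAP 7.4 also summarises Day -2 and Day -1 events separately. If JUUL events on those days are left out of its column, the ratio is 69/15 = 4.6.
- Counting use days only gives 55/3 = 18.3.

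**Non-switchers against continue-smoking.** 71/69 = 1.03, so this contrast is hardly touched.

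**Switchers.** The documents give no switching rate. Assume 40 starters per e-liquid (the SAP section 3 figure), with 10 switching out and 10 switching in. The column then holds 50 subjects: 30 with 69 days, 10 with 27 days and 10 with 42 days. At h = 1% per day the component percentages are 49.8%, 23.7% and 34.3%:

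(30 × 49.84 + 10 × 23.66 + 10 × 34.30) / 50 = 41.5%

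Continue-smoking shows 1 - exp(-0.71) = 50.8%. The same formula at other assumed hazards:

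| Hazard per day | 69 d | 27 d | 42 d | Myblu column | Cigarettes (71 d) |
|---|---|---|---|---|---|
| 0.5% | 29.2% | 12.6% | 18.9% | 23.8% | 29.9% |
| 1% | 49.8% | 23.7% | 34.3% | 41.5% | 50.8% |
| 2% | 74.8% | 41.7% | 56.8% | 64.6% | 75.8% |

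With half switching at 1% per day: (20 × 49.84 + 20 × 23.66 + 20 × 34.30) / 60 = 35.9% against 50.8%.

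**Table 14.3.1.2.** Its percentages are of total events, so the ratios above do not apply to them. There the unequal windows affect the raw counts.

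**The case against.** The AE tables are descriptive and no test is planned. Objective 10 names no JUUL comparison. JUUL is the comparator for nicotine uptake in objective 9, and the control for the main study is continue-smoking (Protocol 3.2). A separate report on the PK sub-study is intended (Protocol 8.5.2). All of this stands, so distortion of the JUUL column does not bear on a planned safety conclusion.

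Equal hazards are also doubtful. JUUL's 17 days include first exposure in confinement and PK blood sampling in all 20 subjects. Myblu first exposure goes to the Product Trial column, and only up to 20 of about 43 subjects per e-liquid enter the PK sub-study. In the earlier myblu study, puncture site pain was the most frequent AE (Protocol 1.2). This stands too, and it limits any remedy. A rate per person-day could overstate JUUL. Restricting Products A to E to their first 17 days would set post-trial use against a JUUL window of which about 14 days follow discharge. That restriction should not be required.

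The size of the switcher effect depends on an unknown switching pattern. With 20% leaving an e-liquid and none joining, at 1% per day, the column is 0.8 × 49.8 + 0.2 × 23.7 = 44.6% against 49.8% without switching, a ratio of only 1.12. Similar switching across e-liquids would largely cancel between them. It would not cancel against cigarettes, because that column has no switchers.

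Finally, the listings carry onset dates and times, so a reader could derive rates. That does not repair a summary table whose columns cannot be compared as printed.

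**Conclusion.** The point holds as a reporting weakness that is cheap to correct. As planned, equal AE rates would produce unequal percentages: up to about 4-fold between JUUL and myblu non-switchers for infrequent events, and a drop from about 51% to about 41% in a myblu column relative to cigarettes in the 25% switching example.

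These sizes rest on three assumptions: an equal constant hazard; assumed hazards and switching rates; and follow-up events counting for the last product used, which SAP 7.4 states only for events with a missing onset time. The inequality of the windows does not depend on the assumed hazard or switching rates.

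A reader might infer that the tables will make JUUL look safer than myblu, or that they undermine objective 10 as a whole. The documents support neither. No JUUL safety comparison is planned, early-exposure and procedure-related events could push the JUUL percentage the other way, and the contrast between non-switchers and continue-smoking is nearly balanced at 69 against 71 days. No hypothesis test is affected.

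**What to change.** In SAP 7.4 and the shells:

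- Table 14.3.1.1: keep the crude percentages. For each product column, add person-days of observation and subjects with a first event per 100 person-days. Count the days for this rate only up to the first event. If total days were used at an equal hazard of 1% per day, JUUL would show 15.63/17 = 0.92 and a myblu non-switcher 49.84/69 = 0.72 per 100 days, so some of the distortion would remain.
- Table 14.3.1.2: add events per 100 person-days, using total days.
- Split switchers' person-time at the switch date, and state to which product all follow-up events belong, not only those with a missing onset time.
- State whether JUUL events on Day -2 and Day -1 stay in its column.
- Footnote the JUUL column with its observation window, and say that its rates are not directly comparable because they cover first exposure and PK procedures, whereas myblu first exposure is in the Product Trial column.

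The cost is a few SAP sentences, two extra rows in Table 14.3.1.1, one in Table 14.3.1.2, and footnotes, all from dates already recorded. The downside is that rates per person-day assume a roughly constant hazard, which is why the crude percentages should stay beside them.

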# 7.5 Clinical Laboratory Tests (Serum Chemistry, Hematology, and Urinalysis)

Serum Chemistry, hematology, and urinalysis samples will be collected at screening and check-in (Day -2) for all product arms. For *my*bluTM and continue-smoking arms, the clinical laboratory tests will also be performed at the end of Period 1 (Day 29) and the discharge from the study (Day 57, Period 2) or upon early termination.

Descriptive statistics will be reported for numeric clinical data and change from baseline by product arm and time point. Rechecked values prior to randomization will be used in calculating summary statistics. Baseline is the last non-missing value including recheck and unscheduled event before randomization (usually on Day -2 Check-in). Normal ranges will be listed.

Out of normal range and clinically significant laboratory values will be listed by subject. Results that are indicated as CS by the PI will be listed in the table.

A urine cotinine test will be completed at Screening and Check-in (Day -2) for all product arms. For *my*bluTM and continue-smoking arms, the urine cotinine test will also be performed on the first day of each Test Visit.

Urine drug tests and alcohol breath tests will be completed at Screening and Check-in (Day -2) for all product arms.

For females, serum pregnancy tests will be completed at Screening and urine pregnancy tests will be completed at Check-in for all product arms. For *my*blu™ and continue-smoking arms, the urine pregnancy tests will also be performed on the first day of each Test Visit. Results for these tests will be listed as "Negative" or "Positive."

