4.5 Subject Randomization and Product Assignments

Each subject will be assigned to a study arm (*my*bluTM, continue-smoking, JUUL[®]) according to the randomization plan. The study arms will be stratified by sex (male or female) and age class (≤ 40 years of age, > 40 years of age). Each sex and age class should not account for more than 65% of the randomized population in each arm, and the Caucasian race should not comprise more than 80% of the randomized population in each arm. For logistical and operational reasons, the first subject in each sex-age class stratum who successfully completes the screening procedures at each site may be assigned to the JUUL[®] arm.

For the main study, a sufficient number of subjects are intended to be randomized to better ensure that at least 29 subjects in each of the *my*bluTM e-liquids and the continue-smoking arm complete the Day 28 study assessments. To account for potential attrition, up to 175 subjects are planned to be randomized into the *my*bluTM arm (with approximately 43 subjects intended to be assigned to each *my*bluTM e-liquid) and up to 40 subjects will be randomized into the continue-smoking arm. Assignment of subjects to a specific *my*bluTM product will be based on subject product preference. An attempt will also be made to apply the sex and age class stratification to each product in the PK sub-study, though the same potential challenges will apply.

For the PK sub-study, up to 20 subjects assigned to each mybluTM e-liquid, 20 subjects in the continue-smoking arm, and all 20 subjects in the JUUL[®] arm will be selected to participate. An attempt will also be made to apply the sex and age class stratification to each product in the PK sub-study, though the same potential challenges will apply.

Subjects randomized to the *my*bluTM or continue-smoking arms must not be informed of their arm assignment until completion of baseline assessments to avoid changes in behavior that might impact those assessments. Therefore, subjects should be prepared to stay in the clinic through Day 5 with the understanding that they may be discharged from the test visit early depending on which arm to which they are randomized. As subjects in the JUUL[®] arm will only participate from Days -2 through 1, these subjects may be informed once the assignment is made.

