	12-lead ECG	Subjects must be supine for at least 5 minutes prior to measurement, must be collected at least 15 minutes after the last cigarette smoked.
	Vital signs	Subjects must be seated for at least 5 minutes prior to measurement, must be collected at least 15 minutes after the last cigarette smoked.
	Blood collection for clinical chemistry, hematology, serology, FSH (post- menopausal females) and serum pregnancy test (females)	Blood collection must be preceded by an 8-hour fast.
	Spirometry	To be performed after completion of the assessments listed above, and must be preceded by a minimum 60-minute abstention from cigarette smoking.
	Review of tobacco and nicotine restrictions	
	Smoking cessation information provided	

6.1.2 Baseline and Product Use Period 1

Upon successful completion of Screening, subjects who continue to meet study requirements will be scheduled to check in to the clinic for Test Visit 1 on Day -2 at a time designated by the clinic staff (check-in for JUUL[®] arm should be as early in the day as possible to maximize the time to use the product) and will remain in the clinic until completion of all study events as required by their randomization arm. Reminder telephone calls will be made to the subjects 24 to 48 hours prior to the test visit. Subjects who fail the check-in requirements will be considered a "screen failure" and will be excluded from participation. For the *my*bluTM and continue-smoking arms, the Baseline Period will consist of the time between check-in and first product use on Day 1. The following table provides the general clinic schedule for Test Visit 1. The procedures listed should be performed for subjects as appropriate for the randomization arm.

Time	Procedures	Comments
Day -2		
	Check-in events	
	Urine collection for urinalysis, drug, cotinine, and pregnancy (females) tests Alcohol breath test Exhaled CO measurement	Subjects must have negative drug, alcohol, and pregnancy tests, and have acceptable cotinine and exhaled CO results prior to completing the remaining assessments. Exhaled CO will be measured within 1 hour of check-in.
	Blood sample collection for clinical chemistry and hematology	JUUL [®] arm, following a minimum 8-hour fast.
	Vital signs	Subjects must be seated for at least 5 minutes prior to measurement, must be collected at least 15 minutes after the last study product used.
	Update medical history, and tobacco use history/usual brand cigarette documentation	

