	Update medications	Throughout the day
	Symptom-driven physical examination	
	Body weight documentation	
	Additional demographics documentation	
	Review of inclusion / exclusion criteria	
	Review of in-clinic tobacco and nicotine restrictions	Any time prior to the start of product use
Immediately following check-in	Training on JUUL® product	JUUL® arm only
Through 23:00	Product use	
	Document AEs	To begin following first study product use
14:00 - 15:00	Start of 24-hour urine collection	my blu™ and continue- smoking arms only
17:00 - 18:00	Blood sample collection for COHb	my blu [™] and continue- smoking arms only

Table 5Test Visit 1 Schedule

Time	Procedures	Comments
20:00 - 22:00	Questionnaires administered (PSCDI, Cough, QSU-Brief, MTWS-R, PES, Product Liking, Future Intent to Use, Product and Health Effects Perceptions)	my blu [™] and continue- smoking arms only. Subjects must be allowed a period of at least 2 hours of product use prior to questionnaire administration.
Day -1		
	Document medications	Throughout the day
	Blood sample collection for clinical chemistry, hematology, and BoPH/bio-banking	my blu [™] and continue- smoking arms, following a minimum 8-hour fast and prior to the start of product use
07:00 - 23:00	Product use	
14:00 - 15:00	End of 24-hour urine collection	\pm 30 minutes from the start time on Day -2, my blu TM and continue-smoking arms only
After urine collection	FeNO	Must be preceded by a minimum 1 hour food and water restriction and a 30-minute abstention from study product use. my blu [™] and continue-smoking arms only
~18:00	Discharge continue-smoking subjects not participating in PK assessments following completion of baseline assessments Symptom-driven physical Vital signs Review of tobacco and nicotine restrictions Subject cigarettes returned	Discharge events may be completed prior to 18:00
Day 1		
	Document AEs and medications	Throughout the day
	Product demonstration and training	my blu™ arm only
Through 23:00	my blu™ product use	To begin following product demonstration and training
09:00	Fixed puffing PK session	Continue-smoking and JUUL [®] arms, follows a 10-hour abstention from product use.

Product use documentation

Time	Procedures	Comments
	Blood sampling	Per sampling schedule
15:00	Ad libitum puffing PK session	Continue-smoking and JUUL [®] arms, to begin ~6 hours following the start of the fixed puffing regimen.
	Product use documentation	

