To further improve compliance through Day 56, during the Day 28 visit subjects using a mybluTM product may be allowed to choose to switch to the alternate nicotine strength of their current flavor, to switch to the alternate flavor with the same nicotine strength as their initial choice, or to continue using the same e-liquid selected initially. Subjects will be allowed a brief trial with the alternate products if desired. The site staff will document this use, but subjects will not need to report these as a part of their product use reporting.

Usual Brand Cigarette Use

Subjects randomized to the continue-smoking arm will smoke their usual brand cigarettes throughout each confinement visit. Subjects will turn-over all cigarettes upon check-in to each test visit.

JUUL[®] Product Use

Subjects in the JUUL[®] arm will begin using the product following the demonstration and training on Day -2 and will continue to use the product through 23:00 on Day -1. Subjects in the JUUL[®] arm will not be allowed to smoke at any time from the time of check-in on Day -2 through discharge on Day 1.

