6.4 Biomarker Sample Collection

6.4.1 Blood

Blood samples for COHb in whole blood (2 x 4 mL), sICAM in plasma (1 x 4 mL), WBCs in whole blood (measured in hematology sample), HDL-C in serum (1 x 3.5 mL), MCP-1 in serum (1 x 3.5 mL), and serum for bio-banking (up to 17 mL) will be collected during Test Visits 1, 3, and 5. Samples for COHb will be collected in the afternoon and samples for the other biomarkers and bio-banking will be collected following an overnight fast of at least 8 hours.

Up to approximately 118 mL of blood will be required for the planned assessments during the entire study.

Detailed instructions for collection, processing, and shipping of blood samples will be provided separately.

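### SAP 7.5 places main-arm chemistry and hematology on the wrong day, and its pre-randomization baseline rule would exclude the Day -1 pre-product sample if randomization takes place by Day -2

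*SAP*

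**What the plan says.** **SAP 7.5.** On timing: "Serum Chemistry, hematology, and urinalysis samples will be collected at screening and check-in (Day -2) for all product arms". On baseline: "Baseline is the last non-missing value including recheck and unscheduled event before randomization (usually on Day -2 Check-in". Later main-arm laboratory samples are placed at Day 29 and Day 57, and change from baseline is summarized descriptively by arm and time point.

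**Protocol Table 5 (Section 6.1.2).** The Day -2 block has an entry "Blood sample collection for clinical chemistry and hematology", labelled for the JUUL arm. The Day -1 block has "Blood sample collection for clinical chemistry, hematology, and BoPH/bio-banking", labelled for the myblu and continue-smoking arms, fasting and before product use starts. Table 2, which covers the two main arms, also marks chemistry and hematology under Day -1. It puts urinalysis under Day -2.

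**Protocol on assignment.** Under Section 4.5, main-arm subjects "must not be informed of their arm assignment until completion of baseline assessments". Section 6.1.2 says of Test Visit 1, which starts on Day -2: "The procedures listed should be performed for subjects as appropriate for the randomization arm". Under Section 6.3.1, subjects in the JUUL "arm will begin using the product following the demonstration and training on Day -2".

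**White cell count.** Protocol 6.4.1 lists, among the biomarker blood samples, "WBCs in whole blood (measured in hematology sample". It is therefore both a safety laboratory value and a biomarker of potential harm (BoPH).

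SAP Section 8 states that the SAP's analyses agree with the protocol's.

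**The concern.** The SAP's baseline rule assumes a Day -2 blood sample that the protocol does not schedule in the two main arms. The sample that is scheduled there, on Day -1, is the natural baseline: it is fasting, is taken in the clinic, and comes just before the switch on Day 1. Whether the rule admits it depends on when randomization happens, which neither document states.

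If the rule shuts the Day -1 sample out, the safety laboratory changes are measured from an older sample taken to establish eligibility. The same hematology draw could then serve as the white cell baseline in the BoPH tables while a screening value serves in the safety tables. A programmer working from SAP 7.5 alone cannot tell which result is intended.

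**Working it through.** The plan gives no figure to reproduce. The check compares the schedules and counts days.

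**1. Sampling day**

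| Sample | SAP 7.5 | Protocol Tables 2, 3 and 5 |
|---|---|---|
| Chemistry and hematology, myblu and continue-smoking | Day -2 | Day -1 |
| Chemistry and hematology, JUUL | Day -2 | Day -2 |
| Urinalysis, all arms | Day -2 | Day -2 |

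The conflict is confined to chemistry and hematology in the two main arms. It exists whatever the time of randomization.

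**2. When randomization occurs**

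These points favor Day -2 or earlier:
- Section 4.5 conceals the assignment from main-arm subjects until baseline assessments are complete, so it appears to exist before then.
- Test Visit 1 procedures follow the randomization arm from Day -2. Table 5 marks the Day -2 urine collection, COHb sample and questionnaires as not for JUUL.
- One plan assigns all three arms (Section 4.5), and JUUL use starts on Day -2.
- Section 4.3.1 gives dietary advice covering the two days before Test Visit 1 to subjects already described as randomized to the main arms.
- Section 6.2.9 puts the eligibility exhaled CO before randomization. That measurement is made at check-in, so it is compatible with randomization later on Day -2.

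None of these gives a day or time, so the timing is an inference.

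**3. Result under each timing**

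- *Randomized by Day -2.* The Day -1 draw comes after randomization and fails the rule. Baseline becomes the last screening, recheck or unscheduled value obtained before randomization.
- *Randomized on Day -1 after the draw.* The Day -1 value qualifies. Only the collection-day sentence and the remark that baseline is usually Day -2 are wrong.

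**4. Days involved** (nominal days; the schedule has no Day 0; visit windows ignored)

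Input: screening is at most 28 days before Day -2 (Protocol 6.1.1).

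- Oldest screening sample to the Day -1 draw: 28 + 1 = 29 days.
- Day -1 draw to Day 29: 1 + 28 = 29 days.
- Oldest screening sample to Day 29: 29 + 29 = 58 days.

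In the worst case, the interval over which the Day 29 change is measured doubles from 29 to 58 days.

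**5. Subjects**

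Protocol 3.1 allows up to 175 in the myblu arm and 40 in continue-smoking: 175 + 40 = 215. JUUL subjects have no later scheduled laboratory draw (Protocol Table 3), so no scheduled change from baseline arises there.

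**6. White cell count**

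The SAP's biomarker summary shell (Table 14.2.2.1.1.1) allows a Day -1 baseline for some endpoints, and the BoPH blood is drawn on Day -1. SAP 7.5 governs the same analyte in the safety tables. Under the first timing in step 3, the two baselines differ.

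**The case against.** The strongest reply is that main-arm randomization before the Day -1 draw is not documented. Section 4.5 only says when subjects may be told. JUUL timing need not settle main-arm timing, because the first subject in each stratum at a site may simply be placed in JUUL for logistical reasons, and the protocol's definition of study arms speaks of subjects randomized to the other two arms but assigned to JUUL. In Table 5 the first scheduled step that separates myblu from continue-smoking is the discharge at about 18:00 on Day -1, after the morning draw. This stands, and it is why the conclusion is conditional. A reader might infer that the SAP definitely discards the Day -1 baseline in every main-arm subject; the documents do not establish that.

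The SAP's intent also points the other way. Its parenthetical expects a Test Visit 1 sample, its Section 3 runs the main-arm Baseline Period from check-in to first product use on Day 1, and its laboratory shell (Table 14.3.5.1) keeps screening and check-in as separate time points. That is a fair reading of intent, but the operative rule still refers to randomization.

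A reader might also infer that regression to the mean from an eligibility sample would appear as a product effect. The documents do not support a size for this. Section 6.2.8 admits values outside the normal range if the investigator judges them not clinically significant, and the only numeric limit tied to these tests is the creatinine-clearance criterion in Section 4.2. The continue-smoking arm has the same rule and schedule, so any such drift should appear there too.

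**Conclusion.** The collection-day conflict between SAP 7.5 and Protocol Tables 2 and 5 is established and needs no assumption. The loss of the Day -1 baseline is conditional on randomization preceding that draw, which is the better-supported reading but is stated nowhere. On that condition, this is a wrong rule and more than a missing detail: it replaces the pre-product sample with a value up to 29 days older, and white cell count could carry two baselines in one report.

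The reach is limited to descriptive chemistry and hematology change-from-baseline tables in the two main arms, at most 215 subjects. The urinalysis baseline is unaffected because both documents place that sample at Day -2 check-in. The primary endpoints are not governed by this rule. The point deserves correction because it is cheap to settle, but it does not threaten the trial's main conclusions.

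**What to change.** Make two changes to SAP 7.5:

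1. Correct the collection-day sentence to match Protocol Tables 2 and 5: chemistry and hematology on Day -1 for myblu and continue-smoking and on Day -2 for JUUL, with urinalysis on Day -2 in all arms.
2. Replace the baseline rule. For myblu and continue-smoking, use the last non-missing value, counting rechecks and unscheduled samples, obtained prior to Day 1 product use. For JUUL, use the last non-missing value before first JUUL use on Day -2.

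The main-arm rule should name Day 1. A rule based on first use of the assigned product would be ambiguous in the continue-smoking arm, whose product is smoked throughout baseline; Protocol 7.6 itself speaks of first study product use on Day -2. SAP 6.4.2 already anchors the subjective-measure baseline to Day 1 product use, so the change brings the sections into line. It also makes the laboratory baseline independent of the unstated randomization time and lets the safety and BoPH tables share one white cell baseline.

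The cost is two SAP sentences, plus mapping the check-in row of the laboratory shell to the Day -1 draw in the main arms. No new data are needed.
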